7.8 Flow-chart of trial procedures

Figure 3: flow chart trial procedures

7.9 Long term follow-up assessments

Not applicable

7.10 Qualitative assessments – Nested studies

A process evaluation will be nested within the pragmatic clustered randomized trial. The process evaluation will capture data to understand how the intervention is used and viewed by GP and patients. This is important for informing implementation in practice. It will explain how GPs and patients experience the intervention. We aim to identify factors within each arm which influence the ability (or inability) to withdraw from benzodiazepines whilst taking part in the blended care program or whilst receiving usual care in order to build a framework describing the mechanisms required for successful implementation.

Individual interviews will be conducted with GPs and patients taking part in the trial. Interviews will be carried out to capture perceived barriers and facilitators to using the blended care approach or with the usual care approach. GPs (approximately 8) will be purposively sampled to obtain variation in gender, practice setting and experience. Patients (approximately 14-18) will be purposively sampled to obtain variation in age, gender, and how successful the withdrawal has been. Interviews will follow semi-structured topic guides exploring GPs' and patients' views and experiences of taking part in the trial. Topic guides will be informed by existing literature and theory of health behaviour to ensure that questions elicit likely key determinants of behaviour. Topic guides will be piloted with patient representatives and clinicians. Interviews will be carried out face to face and analysed using thematic and Framework analysis.

7.11 Withdrawal criteria

Withdrawal from the study can be initiated either by the patient or by the general practitioner.

As stated in the Informed Consent patients have the right to end her/his participation in the trial at any point in time and for any reason. In case a patient wishes to end her/his participation, she/he can do so either by notifying her/his GP or by ticking the box that will be provided in each e-questionnaire allowing patients to communicate their wish to withdrawal.

The treating GP can also consider a patient for withdrawal from the study. However, the GP will have to discuss this option with the study coordinator and to receive the consent of the latter before the final decision of withdrawal can be made.

In all instances, the reason for withdrawal will be asked for and notified.

Withdrawn patients will not be replaced. For statistical handling of withdrawn patients see section 10.3.4.

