3.4 Primary endpoint

The primary outcome is the proportion of subjects with a negative benzodiazepine urine test assessed 12 months after initiation of the intervention.

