7.7 Trial assessments

Within the week following the enrolment of the 10th patient by the GP(s), the general practice will be allocated to either the blended care or usual care arm.

During the baseline visit, which will take place within 12 weeks after the screening visit, the GP will start the intervention, which will be either usual care or blended care for the discontinuation of benzodiazepines.

Assessment by GP

After the baseline visit, appointments –minimal 1- for follow-up and prescription renewals will be scheduled left at the discretion of the GP and depending on the needs of the patient until the end of dose reduction. In addition to these scheduled appointments, patients will be allowed to request an extra appointment with their GP when needed. This approach maximally reflects daily practice as should be in a pragmatic trial. The GPs will be asked to note in the Electronic Health Record (EHR) at each contact with the patient the (z-)BZD-related interventions delivered to the patients via standardized entry fields, and to document this data in the eCRF.

These interventions may include:

- Advise to discontinue (z-)benzodiazepines
- Discussion of tapering schedule
- Discussion of withdrawal symptoms
- Discussion of sleep quality

- Discussion of coping strategies, triggers and facilitators
- Decrease of benzodiazepine dose
- Increase of benzodiazepine dose

In the exceptional circumstances of COVID-19, EC Research allows the PI or his delegate to use telemedicine visits. This means that the GP can perform a consultation by telephone or video conference. As with regular consultations, all (z-)BZD interventions need to be documented in the EHR and eCRF of the patient.

E-questionnaires

Patients will be requested to complete the following e-questionnaires at weeks 6, 12, 26 and 52 comprising of the validated EQ5D-3L, Audit-C and Insomnia Severity Index. Furthermore, the e-questionnaire will include questions about self-reported use of (z-)BZD and other psychoactive medication, self-reported falls and use of medical services in the past period.

The questionnaires will be e-mailed to the study participants at week 5, 11, 25 and 51 with the request to complete them within 2 weeks. A reminder will be sent after 1 week to all participants who have not responded yet and every week after until response or the deadline

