10.3.4 Procedure(s) to account for missing or spurious data

See section 7.7 for strategies to maximise follow-up and to prevent missing data.

When a patient withdraws from the study prematurely, all data collected up until the moment of withdrawal will be analysed (using the intent-to-treat approach). In case the data for measurement of the primary endpoint was not collected, the outcome will be classified as failure or continued benzodiazepine use in the intent-to-treat analysis. After withdrawal, no further data of this patient will be collected.

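### Patient withdrawal has a single level: whoever ticks the withdrawal box, or tells the GP, before the week-52 urine sample gives no further data and is counted as a failure.

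*Combined protocol and SAP*

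**What the plan says.** Section 7.11 (Withdrawal criteria) gives the patient two ways out: "In case a patient wishes to end her/his participation, she/he can do so either by notifying her/his GP", or "ticking the box that will be provided in each e-questionnaire allowing patients to communicate their wish to withdrawal". The reason is asked for in every case. Withdrawal proposed by the GP needs the study coordinator's agreement; no comparable step is written for the patient's own decision, and no partial form of withdrawal is described.

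Section 10.3.4 sets the consequences. Data gathered before withdrawal are analysed, but "After withdrawal, no further data of this patient will be collected". For a primary endpoint that was not obtained, "the outcome will be classified as failure or continued benzodiazepine use in the intent-to-treat analysis".

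Section 3.4 defines that endpoint: "The primary outcome is the proportion of subjects with a negative benzodiazepine urine test assessed 12 months after initiation of the intervention". Section 7.7 gives the timing: "Patients will be requested to complete the following e-questionnaires at weeks 6, 12, 26 and 52". Urine samples are requested separately, by invitations at weeks 25 and 51, with their own reminders and a voucher. They are given at the practice, and no GP consultation is needed.

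**The concern.** The questionnaires and the urine test are separate procedures, yet the only exit described covers both. A patient may want no more questionnaires and still be willing to give one urine sample at 12 months. If that patient ticks the box, the plan gives up an obtainable primary outcome and replaces it with an imputed failure. It also gives up the prescription data, although section 3.3 prefers routinely collected outcomes.

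If such withdrawals were equally common in both arms, the effect would be mild dilution. If they were more common in one arm, the primary comparison would be biased. The arms do differ in what they ask of patients, since only the blended arm has the e-tool (section 8.1). Section 10.3.4 names no sensitivity analysis for the failure rule, so no planned analysis would show the distortion.

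**Working it through.** **Step 1. The rules in sequence.**
- The box, or a word to the GP, ends participation (7.11).
- Nothing is collected afterwards (10.3.4).
- A missing 12-month urine result counts as failure (10.3.4).

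Every link is stated in the text. The chain applies to a patient who withdraws before giving the week-52 sample. A sample given earlier is kept.

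**Step 2. When it can happen.** The questionnaires at weeks 6, 12 and 26 clearly precede the week-52 sample. The fourth is e-mailed at week 51, the same week as the urine invitation, so a tick there may come before or after the sample.

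**Step 3. The plan's own sample size (10.1).** Inputs are 15% versus 25%, alpha 0.05 (two-sided, which reproduces the figure), power 80%, 10% loss, ICC 0.11 and cluster size 10.
- A two-proportion calculation with continuity correction gives 270 per arm.
- 270 x 1.10 = 297 per arm, or 594 in total.
- Design effect = 1 + 0.11 x 9 = 1.99.
- 594 x 1.99 = 1182; 1182/10 = 118.2, so 119 GPs.

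The stated figures reproduce. The effective size per arm is 1182/2/1.99 = 297.

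**Step 4. Equal loss, scored as failure.** The observed rate in an arm is p x (1 - d), where p is the true rate and d the share without a result.
- At the planned d = 10%: 0.15 x 0.90 = 13.5% and 0.25 x 0.90 = 22.5%, a difference of 9.0 points. Power is 78.6% with continuity correction and 81.6% without.
- At the 7% loss that section 10.1 cites from an earlier cluster trial: 13.95% and 23.25%, a difference of 9.3 points.

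Equal loss at these levels costs little.

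**Step 5. Unequal loss.** Shift in the difference = excess withdrawal x share of those patients who had in fact stopped. The excess is assumed to be 5 percentage points; the share is taken from the planned rates, 15-25%.
- 0.05 x 0.15 = 0.75 points.
- 0.05 x 0.25 = 1.25 points.

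With 591 patients per arm (1182/2), an excess of 5 points is about 30 patients (591 x 0.05 = 29.6). Of these, 4 to 7 would be true discontinuers scored as failures (29.6 x 0.15 = 4.4; 29.6 x 0.25 = 7.4).

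**Step 6. Direction and power**, against an assumed loss of 5% in both arms:

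| Loss, control / blended | Observed rates | Difference | Power, with / without continuity correction |
|---|---|---|---|
| 5% / 5% | 14.25% / 23.75% | 9.5 points | 81.4% / 84.1% |
| 5% / 10% | 14.25% / 22.5% | 8.25 points | 70.3% / 73.9% |
| 10% / 5% | 13.5% / 23.75% | 10.25 points | 87.6% / 89.6% |

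An excess in the blended arm pulls the result toward no effect (9.5 - 8.25 = 1.25). An excess in the control arm favours blended care (10.25 - 9.5 = 0.75). If the true rate were 15% in both arms, 5% versus 10% loss would by itself produce a difference of 0.15 x 0.05 = 0.75 points.

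**The case against.** Much of the case on the other side stands, and it limits the point.

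- **Questionnaire fatigue is not withdrawal.** A reader might infer that any patient tired of questionnaires forfeits the urine test. Section 7.7 does not support that. An unanswered questionnaire brings reminders up to a deadline and then counts as missing, while the urine invitation still goes out.
- **Stopping the e-tool is not withdrawal.** Patients work through the module at their own pace (Trial Summary), visits are tracked as compliance (8.2), and e-tool use is a subgroup variable (10.3.2). A patient can stop using it, stay enrolled and be analysed by intention to treat. Section 7.11 does not say so explicitly.
- **The wish could be clarified.** The box communicates a wish and the reason is asked for, so contact with the patient is possible. No offer of reduced follow-up is written, however. The wording of the box is not in the documents, and the consent pages are not in the review copy, so a graded option there cannot be ruled out.
- **The imbalance is hypothetical.** A 5-point gap from this route alone is half of the 10% total loss that section 10.1 allows for. The documents do not say how much loss would come through the box. The mechanism suggested by the e-tool points to an excess in the blended arm; none is documented for the control arm.
- **Larger shifts are not supported.** A reader might assume that up to half of those who withdraw have stopped, giving 2.5 points. That is twice the planned blended-arm rate and has no basis in the documents.
- **Not every avoided withdrawal yields an outcome.** The patient must still come to the practice to give urine, and prescription data serve only a secondary endpoint.

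None of this changes the rule for a patient who does withdraw before the week-52 sample.

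**Conclusion.** The point holds for patients who tick the box or tell the GP before giving the week-52 sample: no further data are collected and the primary outcome becomes a failure by rule. The size cannot be derived from the documents. Under an assumed 5-point excess in one arm and the plan's own 15-25% discontinuation rates, the shift is about 0.75-1.25 points, or 7.5-12.5% of the 10-point target, with the direction set by the arm that has the excess. This is a retention weakness that is cheap to repair. It is not an arithmetic error, and the documents do not show that the primary comparison is seriously biased. The absence of a sensitivity analysis for the failure rule affects every missing urine result and is a wider matter than this box.

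**What to change.** 1. In 7.11 and in the e-questionnaire, record the level of withdrawal when a patient ticks the box or tells the GP: (a) no more questionnaires, with the 6- and 12-month urine invitations and GP prescription data continuing if the patient agrees; or (b) no more data at all.
2. State in 7.11 that stopping the e-tool is not withdrawal from the study.
3. Change 10.3.4 so that only (b) ends data collection.
4. Align the consent text.

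The right to withdraw fully is unchanged. The cost is one questionnaire item, edits to two sections and the consent text, and an ethics notification. An explicit option (a) may also slightly reduce the EQ-5D-3L and self-report data, which are secondary. The gain is limited to patients who choose (a) and then give a urine sample; each of them contributes a measured primary outcome in place of an imputed failure.

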7.12 End of trial

Where necessary, end of trial documents and notifications will be drafted and presented.

8 TRIAL INTERVENTION / MEDICATION

8.1 Name and description of intervention(s)

Care as usual

In the control arm, patients will receive 'usual care' left at the discretion of the treating GP.

Apart from the general training session for all participating GPs they have attended prior to recruitment and randomization, GPs in the control arm will not receive additional tools.

They are expected (but not forced) to follow the Belgian guidelines (as described in "Anxiety, stress and sleeping problems. A toolkit for general practitioners" and "Sleeping pills and sedatives. How can you assist your patients in the search for other solutions?"), which recommend a stepped approach.

In first instance a minimal intervention strategy is applied which may consist of a discontinuation letter or a single discontinuation advice during a consult. In both instances information about the consequences of (z-)BZDs is given aiming at encouraging the patient to discontinue (z-)BZD use along with a (z-)BZD tapering scheme. In case the minimal intervention failed or in case the GP judges the chance of a successful minimal intervention to be unlikely, a brief intervention is recommended which may span one or more consults. During this intervention, the GP will -based on the principles of motivational interviewing- assess the patient's readiness for change and match the appropriate intervention. Once the patient is ready for withdrawal a patient-tailored (z-)BZD tapering scheme will be developed which typically consists of a 10–20% reduction in the daily dose of the (z-)BZD every 2–4 weeks. To facilitate withdrawal a switch from a (z-)BZD with a short half-life to diazepam may be considered.

Blended care

In the intervention arm an interactive e-learning program is blended with direct contacts face-to-face with the treating GP.

The GPs will provide patients participating in the study access to an interactive e-learning module delivered through a web-based platform, which patients and GPs can access securely with a personal login account. The e-tool used in this trial will be a newly designed tool, inspired by the program of slaapzorgeloos.be that was developed for a pilot trial described in section 2, and which was based on evidence resulting from a review of the literature, and other websites such as www.benzodebaas.nl and www.sleepio.com, which also focus on sleeping problems and/or benzodiazepine use.

During the preparatory phase of the trial the program of slaapzorgeloos.be was adapted including improvement of lay-out, user friendliness and content using the think-aloud method and MoSCoW analysis. During think-aloud interviews, patients and GPs are observed using the e-tool and asked to comment on their reactions to every aspect of e-tool (Bradbury 2014). This enables researchers to identify problems people might experience when using the e-tool and modify it accordingly. They are effective in highlighting navigational difficulties and can reveal useful information relating to the content of an e-tool which needs to be modified (Bradbury 2014). MoSCoW, a prioritisation model used by digital service developers, is a simple tool that can be usefully employed to prioritise the content of an e-tool. Each of the capital letters represents a priority:

- M: Must have this for the intervention to be effective, acceptable and feasible,
- S: Should have (if possible) for the intervention to be a success, but may be able to be delivered in a different way, or is in some way less critical than a Must have,
- C: Could have this as it would be useful, but only if time and resources are available,
- W: Would like for classifying a feature which would be nice, but is not essential now and can be put on hold.

This method ensures efficient development of successful interventions and aids effective communication between team members, who might otherwise perceive different priorities

The adaptation process led to a learning module that consists of 8 informational chapters, a sleeping diary, two conclusive modules and a referral to other informational materials. The learning module aims to empower patients by improving their knowledge, self-efficacy and confidence, enabling them to successfully discontinue their (z-)BZD use.

In the 8 informational chapters, the topics sleep and sleeping disorders, sleeping medication and its associated risks, non-pharmacological alternatives and tapering of (z-)BZDs are addressed.

The sleeping tips, non-medicinal alternatives and coping strategies provided in this module are based on the principles of cognitive behavioural therapy(CBT) which have been proven to be effective in the management of sleeping problems (Ye 2015). CBT is a psychological treatment designed to break the patterns of maladaptive thinking and behaviour that serve to maintain insomnia. CBT comprises a range of techniques including a behavioural component combined with a cognitive and an educational component. In order to encourage active involvement of the patient, interactive components were built in allowing patients to enter information about their sleeping habits, sleep hygiene, coping techniques, triggers and facilitators etc.

During the face-to-face contacts, the treating GP will log in to his panel of the platform, where he will be able to consult the information of each patient separately. Per patient, the GP will see their name, token, the completed eCRFs, and the information from the interventions within the e-tool that was shared by the patient. This facilitates discussing the experiences of the patient and addressing questions the patient may have concerning the contents of the e-tool.

[figure not shown]
Because the learning module will be implemented in Belgium, a Dutch and French version are necessary. For translation, the TRAPD Team Translation Model will be used. A successful translation process is expected to keep the content semantically similar. In case of interactive content as surveys or web based tools, it is also expected to keep the question format similar within the bounds of the target language; retain measurement properties, including the range of response options offered; and maintain the same stimulus (Harkness 2010). Based on growing evidence, a team translation approach is now recommended to design cross-culturally comparable surveys or tools (Harkness 2008, Harkness 2010, Pan 2005 and Willis 2010). The TRAPD Team Translation Model fulfils the criteria for successful translation.

Its procedures are partially iterative. The successive steps are as follow (fig. 4):

- **T – Translation:** two (or more) independent draft translations are produced;
- **R – Review:** the translators and a reviewer compare the draft translations and decide the final translation;
- **A – Adjudication:** an adjudicator (often, the reviewer) compares the reviewed translation with the Master Questionnaire and approves the translation for the pretest or for the fieldwork;
- **P – Pretest:** the adjudicated questionnaire is tested at a small scale. The translation is corrected on the basis of the feedback from the pretest;
- **D – Documentation:** the whole process (draft translations, exchange of comments between the translators, the reviewer and the adjudicator, feedback from the pretest, final translation) is documented.

In this project, translators of the research teams of ULB and ULiege will make the translation of the material from Dutch to French in collaboration. The reviewer will be a staff member of Uliege, and the final adjudication will happen by staff members of ULiege and KULEuven.

Figure 4: The TRAPD translation model

8.2 Assessment of compliance

A built-in system will be developed for the learning module allowing to track users as they visit, leave and return to the e-learning module. Furthermore, each time the user performs specific actions (such as filling in the sleeping diary, answering questions etc.) this will be recorded.

9 SAFETY REPORTING

The risk of adverse events occurring as a consequence of the intervention in this trial is unlikely therefore safety reporting will be limited to the safety reporting that is necessary in routine care (https://www.fagg-afmps.be/nl/notification_effets/humane_geneesmiddelenbewaking/melding_gezondheidszorgbeoefenaars).

10 STATISTICS AND DATA ANALYSIS

10.1 Sample size calculation

The primary research question driving the sample size calculation is whether chronic benzodiazepine users who receive the blended learning intervention are more likely to discontinue (z-)BZD use at 12 months follow-up compared to chronic benzodiazepine users who receive usual care.

The rate of discontinuation by usual care is expected, based on a literature review of RCTs to achieve a rate ranging between 10 and 17%. (Mugunthan K, McGuire T and Glasziou P. Minimal interventions to decrease long-term use of benzodiazepines in primary care: a systematic review and meta-analysis. Br J Gen Pract 2011; 61 (590): e573-e578.)

The study will be powered to detect a statistically significant difference in (z-)BZD discontinuation at 12 months between intervention and control group of 10%, assuming a rate of discontinuation of 15% in the control group

Based on an alpha of 0.05 and 80% power and assuming 10% patients lost to follow-up (In the study by Vicens et al the drop-out rate after 12 months was 7%) an individually randomized study would require a total sample size of 594 participants (297 in each group).

To account for clustering effects from randomized GPs with an intracluster correlation coefficient (ICC) set at 0.11 based on a study by Vicens et al. (C. Vicens, F. Bejarano, E. Sempere, et al. Comparative efficacy of two interventions to discontinue long-term (z-)BZD use: cluster randomized controlled trial in primary care. The British Journal of Psychiatry (2014) 204, 471–479.) and a cluster size of 10 patients, the number of patients required was multiplied by 1.99 corresponding to the cluster design effect ($DE=1+ICC(\text{size of the cluster}-1)$). Thus, the final sample will consist of 1182 patients. Because each general practitioner has to recruit 10 patients, 119 general practitioners are needed.

